4.2.4.2 Definition of start and end dates for time to event variables

Assessment date

Assessment date is defined as for RECIST v1.1 ([CPDR001X2101 Amendment 8 Appendix 14.1.3.2.7]).

Start date

Start date is as defined for RECIST v1.1 ([CPDR001X2101 Amendment 8 Appendix 14.1.3.2.7]).

End dates for time to event variables

The end dates which are used to calculate 'time to event' variables are defined as follows:

- Date of death (during treatment as recorded on the treatment completion page or during follow-up as recorded on the study evaluation completion page or the survival follow-up page).
- Date of death as recorded on death eCRF
- Date of progression as defined in Section 4.2.4.1.
- Date of last adequate tumor assessment is the date the last tumor assessment with overall lesion response of CR, PR or SD which was made before progression or a censoring reason occurred. In this case the last tumor evaluation date at that assessment is used. If no post-baseline assessments are available (before an event or a censoring reason occurred) the date of start of treatment is used.

Note: for sensitivity analyses of time to event endpoints ongoing Subjects with an unconfirmed progression may be censored at time of last assessment.

4.2.4.3 Censoring reason

Censoring reason is derived as for RECIST v1.1 (Table 4-2).

4.2.4.4 Duration of response

Duration of response is defined as a time interval between the first date of confirmed PR/CR and the date of progression as defined in Section 4.2.4.1, or death due to any cause. Intervening assessments of pPD are excluded from the assessment.

Date of confirmed response

Response (irPR or irCR) should be confirmed by a second assessment no less than 4 weeks after the first assessment showing response. Date of response is then the date of the first of these two assessments. For confirmation of irCR the two assessments must be consecutive (intervening assessments of irUNK are permissible). For confirmation of irPR the two assessments do not need to be consecutive, but must not be separated by a pseudo-progression event.

The table below shows a hypothetical data scenarios with programming instructions.

Sequence of assessments	Instructions	
1 irPR	The first PR (assessment 1) is followed by a pseudo-progression	
2 irPD	(assessment 2) and is therefore not confirmed	
3 irPR	Subsequently the Subject has a irPR (assessment 3) which is	
4 irPR	confirmed at the following assessment (assessment 4)	
	The BOR for this Subject is irPR, with date of confirmed irPR equal to the date of assessment 3	

4.3 Event dates used in PFS and DOR

Based on definitions outlined in [CPDR001X2101 Amendment 8 Section 14.1.3.2.9], the following analyses can be considered:

Table 4-2 Options for event dates used in PFS and DOR

Situation		Options for end-date (progression or censoring) ¹	Outcome
		(1) = default unless specified differently in the protocol or RAP	
A	No baseline assessment	(1) Date of randomization/start of treatment ³	Censored
В	Progression at or before next scheduled assessment	(1) Date of progression (2) Date of next scheduled assessment ²	Progressed Progressed
C1	Progression or death after exactly one missing assessment	(1) Date of progression (or death)(2) Date of next scheduled assessment²	Progressed
C2	Progression or death after two or more missing assessments	 (1) Date of last adequate assessment² (2) Date of next scheduled assessment² (3) Date of progression (or death) 	Censored Progressed Progressed
D	No progression	(1) Date of last adequate assessment	Censored
E	Treatment discontinuation due to 'Disease progression' without documented progression, i.e. clinical progression based on investigator claim	(1) N/A (2) Date of discontinuation (visit date at which clinical progression was determined)	Ignored Progressed
F	New anticancer therapy given	, ,	Censored Censored Event Ignored
G	Deaths due to reason other than deterioration of 'Study indication'	(1) Date of last adequate assessment	Censored (only TTP and duration of response)

	,	
•	Options for end-date (progression or censoring) ¹	Outcome
	(1) = default unless specified differently	
	in the protocol or RAP	

- 1. =Definitions can be found in [CPDR001X2101 Amendment 8 Section 14.1.3.2.7]
- 2. =After the last adequate tumor assessment. "Date of next scheduled assessment" is defined [CPDR001X2101 Amendment 8 Section 14.1.3.2.7].
- 3. =The rare exception to this is if the patient dies no later than the time of the second scheduled assessment as defined in the protocol in which case this is a PFS event at the date of death.

5 References

Chen M, Ibrahim J (2006) The Relationship Between the Power Prior and Hierarchical Models, Bayesian Analysis, 1, Number 3.

Deeks ED (2014) Nivolumab: A review of its use in patients with malignant melanoma. Drugs; 74:1233-39.

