#### 14.1.3.2.5 Duration of response

The analysis of the following variables should be performed with much caution when restricted to responders since treatment bias could have been introduced. There have been reports where a treatment with a significantly higher response rate had a significantly shorter duration of response but where this probably primarily reflected selection bias which is explained as follows: It is postulated that there are two groups of patients: a good risk group and a poor risk group. Good risk patients tend to get into response readily (and relatively quickly) and tend to remain in response after they have a response. Poor risk patients tend to be difficult to achieve a response, may have a longer time to respond, and tend to relapse quickly when they do respond. Potent agents induce a response in both good risk and poor risk patients. Less potent agents induce a response mainly in good risk patients only. This is described in more detail by [Morgan \(1988\)](#).

It is recommended that an analysis of all patients (both responders and non-responders) be performed whether or not a “responders only” descriptive analysis is presented. An analysis of responders should only be performed to provide descriptive statistics and even then interpreted with caution by evaluating the results in the context of the observed response rates... If an inferential comparison between treatments is required this should only be performed on all patients (i.e. not restricting to “responders” only) using appropriate statistical methods such as the techniques described in [Ellis et al \(2008\)](#). It should also be stated in the protocol if duration of response is to be calculated in addition for unconfirmed response.

For summary statistics on “responders” only the following definitions are appropriate. (Specific definitions for an all-patient analysis of these endpoints are not appropriate since the status of patients throughout the study is usually taken into account in the analysis).

**Duration of overall response (CR or PR):** For patients with a CR or PR (which may have to be confirmed the start date is the date of first documented response (CR or PR) and the end date and censoring is defined the same as that for time to progression.

The following two durations might be calculated in addition for a large Phase III study in which a reasonable number of responders is seen.

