##### **14.1.4.5.6 Censoring reason**

In order to summarize the various reasons for censoring, the following categories will be calculated for each time to event variable based on the treatment completion page, the study evaluation completion page and the survival page.

For survival the following censoring reasons are possible:

- Alive
- Lost to follow-up

For PFS and TTP (and therefore duration of responses) the following censoring reasons are possible:

- Ongoing without event
- Lost to follow-up
- Withdrew consent
- Adequate assessment no longer available\*
- Event documented after two or more missing tumor assessments (option
- Death due to, see [Table 14-5](#)) to reason other than underlying cancer (*only used for TTP and duration of response*)
- Initiation of new anti-cancer therapy

\*Adequate assessment is defined in [Section 14.1.3.2.7](#). This reason is applicable when adequate evaluations are missing for a specified period prior to data cut-off (or prior to any other censoring reason) corresponding to the unavailability of two or more planned tumor assessments prior to the cut-off date. The following clarifications concerning this reason should also be noted:

- This may be when there has been a definite decision to stop evaluation (e.g. reason="Sponsor decision" on study evaluation completion page), when patients are not followed for progression after treatment completion or when only UNK assessments are available just prior to data cut-off).
- The reason "Adequate assessment no longer available" also prevails in situations when another censoring reason (e.g. withdrawal of consent, loss to follow-up or alternative anti-cancer therapy) has occurred more than the specified period following the last adequate assessment.
- This reason will also be used to censor in case of no baseline assessment.

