Per irRC, irCR, irPR and irPD need to be confirmed with at least two determinations of irCR or irPR or irPD, respectively at least 4 weeks apart. In order to classify overall response as irSD, the patient must have at least one SD assessment (or better) > 6 weeks after start date of study treatment.

Individual lesion measurements and overall response assessments will be listed by patient and assessment date. Best overall response (BOR) per RECIST v1.1 and per irRC will be listed and tabulated.

Overall response rate (ORR) and Disease control rate (DCR)

ORR is the proportion of patients with a best overall response of CR or PR (RECIST v1.1) or of irCR or irPR (irRC). DCR is the proportion of patients with a best overall response of CR, PR, or SD (RECIST v1.1) or of irCR, irPR, or irSD (irRC).

Progression free survival (PFS)

For assessment per RECIST v1.1, PFS is the time from date of start of treatment to the date of event defined as the first documented progression or death due to any cause. If a patient has not had an event, PFS is censored at the date of last adequate tumor assessment ([CPDR001X2101 Amendment 8 Appendix 14.1.3.2.1]). For irRC, PFS is defined similarly, but with the date of event defined as the date of the first documented confirmed progression as defined in Section 4.2.3, or death due to any cause. For irRC, other censoring rules are applied as for RECIST v1.1 ([CPDR001X2101 Amendment 8 Appendix 14.1.3.2.9]).

Duration of response (DOR)

DOR applies only to patients with a BOR of confirmed CR or PR (RECIST v1.1) or of confirmed irCR or irPR (irRC). For assessment per RECIST v1.1, DOR is defined as the time from the date of the first documented response (CR or PR) to the date of first documented progression, or death due to any cause. For assessment per irRC, DOR is defined as the time from the first confirmed response (irCR or irPR), to the date of confirmed progression as defined in Section 4.2.3, or death due to any cause.

Use of alternative cancer therapy

For both RECIST v1.1 and irRC, if any alternative cancer therapy is taken other than palliative radiotherapy any subsequent assessments will be excluded from the analysis of endpoints based on tumor response assessments. If a substantial number of patients receive palliative radiotherapy, sensitivity analyses of these endpoints may be performed where assessments are also censored at the time of palliative radiotherapy.

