3.4.1 Phase I: dose-escalation part

Tumor response will be determined per local investigators' assessment, according to RECIST v1.1 and irRC. Response related efficacy assessments will be defined and analyzed based on both RECIST v1.1 and irRC. The endpoints used to evaluate anti-tumor activity are BOR, ORR, DCR, PFS

For all efficacy parameters, data will be listed, summarized, or analyzed by treatment group.

BOR will be summarized. ORR and DCR will be listed and summarized with accompanying 90% exact binomial confidence intervals.

If appropriate, PFS will be presented graphically using Kaplan Meier plots including all patients treated at RP2D/MTD and by treatment group. Median PFS (in months), 25th and 75th percentiles with corresponding 90% CIs and Kaplan-Meier estimated probabilities (PFS rate) with corresponding 90% CIs at 3, 6, 9, and 12 months will be estimated for each treatment group. DOR will be summarized using the mean, minimum and maximum. PFS, along with DOR for patients who experience a CR or PR at any time on study, will be listed by patient.

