3.4.2 Phase II part

Tumor response will be determined per local investigators' assessment, according to RECIST v1.1 and irRC. Response related efficacy assessments will be defined and analyzed based on both RECIST v1.1 and irRC. The endpoints used to evaluate anti-tumor activity are BOR, ORR, DCR, DOR, PFS using the FAS.

For all efficacy parameters, data will be listed, summarized, or analyzed by treatment group in Phase II.

BOR will be summarized. ORR and DCR will be summarized and listed with accompanying 90% exact binomial confidence intervals. The waterfall plot of best percent change in the sum of longest diameter (SOD) since baseline with annotation of the BOR for RECIST v1.1 will be provided.

PFS will be listed by patient. PFS (per RECIST v1.1 and irRC) will be presented graphically using Kaplan Meier plots including all patients treated at RP2D/MTD and by treatment in Phase II. Median PFS (in months), 25th and 75th percentiles with corresponding 90% CIs and Kaplan-Meier estimated probabilities (PFS rate) with corresponding 90% CIs at 3, 6, 9, and 12 months will be estimated and summarized for each treatment group. The number (%) of events and subjects censored will also be summarized.

DOR will be listed by patient. If there is a large number of patients achieving response (for example, at least 8 responses in a treatment group), the Kaplan-Meier plots for DOR (per RECIST v1.1 and irRC) will also be produced along with the estimation of the respective medians.

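### SAP Table 4-2 row G still censors non-cancer deaths for duration of response although the SAP counts them as events, and the Phase I mean DOR has no rule for censored durations

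*SAP*

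**What the plan says.** **Definition of the DOR event.** For RECIST v1.1, SAP 3.4 runs DOR from first response "to the date of first documented progression, or death due to any cause". For irRC, SAP 4.2.4.4 runs it to "the date of progression as defined in Section 4.2.4.1, or death due to any cause". The SAP change log shows that Addendum 1 introduced any-cause death on purpose.

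**Censoring table.** SAP Table 4-2, in the section on event dates for PFS and DOR, has a row G for deaths from a cause other than the study indication. Its only option is the date of last adequate assessment, with outcome "Censored (only TTP and duration of response"). SAP 4.2.4.3 adds for irRC: "Censoring reason is derived as for RECIST v1.1 (Table 4-2").

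**Protocol.** Row G repeats protocol Table 14-5. Protocol 14.1.3.2.5 says of DOR that "the end date and censoring is defined the same as that for time to progression", and time to progression counts only cancer deaths. The list in protocol 14.1.4.5.6 has a matching censoring reason for non-cancer death, "only used for TTP and duration of response".

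**Summaries.** For Phase I, SAP 3.4.1 says "DOR will be summarized using the mean, minimum and maximum", plus a listing by patient. For Phase II, SAP 3.4.2 plans Kaplan-Meier plots and medians when responders suffice, "for example, at least 8 responses in a treatment group".

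**The concern.** A responder who dies of a non-cancer cause is an event at death under SAP 3.4 and is censored at the last scan under row G. Both rules stand in the current SAP, and the protocol supports the second. A programmer could defend either dataset. Following row G would lengthen DOR relative to the SAP's own definition.

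The Phase I issue is different in kind. The plan treats ongoing responses as censored (Table 4-2 row D and protocol 14.1.4.5.6), yet it asks for an arithmetic mean. A mean needs complete durations. SAP 3.4.1 does not say whether a censored duration is entered as if complete, left out or flagged. The general rule on continuing events in SAP 2.2 concerns completion dates for events such as adverse events and does not settle this.

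**Working it through.** The plan states no figure on this point, so there is none to reproduce. The text is compared first; the sizes that follow are illustrations under stated assumptions.

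**1. Which patients row G affects**

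| Situation of a responder | SAP 3.4 / 4.2.4.4 | Table 4-2 default |
|---|---|---|
| Progression | event | event (row B or C1) |
| Cancer death, fewer than two missed assessments | event | event |
| Non-cancer death, fewer than two missed assessments | event | censored (row G) |
| Death after two or more missed assessments | not addressed | censored (row C2) |
| New anticancer therapy before progression or death | later assessments excluded | censored (row F) |

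The conflict is confined to the third line: non-cancer death with no earlier progression, no new anticancer therapy and fewer than two missed assessments. SAP Table 1-1 does not list time to progression, so row G has no other analysed endpoint to act on.

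**2. Size of the row G effect**

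*Constant hazard.* Suppose a share q of the events ending response are non-cancer deaths. Censoring them leaves a fraction (1 − q) of the hazard, so the median is multiplied by 1/(1 − q), ignoring the small shift from death back to the last scan:

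- q = 5%: 1.05
- q = 10%: 1.11
- q = 20%: 1.25
- q = 30%: 1.43

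*Eight responders*, the number SAP 3.4.2 offers as a guide, with assumed durations of 4, 6, 8, 10, 12, 16, 20 and 24 months. The median is the first time the Kaplan-Meier curve is at or below 0.5.

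- All eight as events: 7/8 × 6/7 × 5/6 × 4/5 = 0.50 at 10 months, so the median is 10.
- The 8-month response ends in a non-cancer death and is censored one month earlier: 7/8 × 6/7 = 0.75 at 6 months, 0.75 × 4/5 = 0.60 at 10, 0.60 × 3/4 = 0.45 at 12. The median is 12.
- Any other one of the four shortest gives the same median of 12. Any one of the four longest leaves it at 10.

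**3. Size of the Phase I effect**

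*Inputs from the documents.* Enrolment began on 27-Apr-2015, and all 58 Phase I patients had been treated by 17-Dec-2015. Two reference dates are used: 06-May-2019 (status date in protocol Amendment 08) and 24-Jul-2020 (SAP date).

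*Assumptions.* Response comes 2–6 months after start, DOR is exponential, and the only censoring is at the reference date.

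*Follow-up from start.* To 06-May-2019 it is 40.6–48.3 months, and to 24-Jul-2020 it is 55.2–62.9 months. Follow-up from response, C, is then:

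- 40.6 − 6 = 34.6 to 48.3 − 2 = 46.3 months, or
- 55.2 − 6 = 49.2 to 62.9 − 2 = 60.9 months,

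taken as uniform over each range.

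*Formulas.* True mean m = median / ln 2. If censored values count as complete, the expected result is E[min(T, C)]. If they are dropped, it is E[T | T ≤ C].

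| Median DOR | True mean | Censored share (2019 / 2020) | Counted as complete | Dropped |
|---|---|---|---|---|
| 12 | 17.3 | 9.9% / 4.2% | 15.6 / 16.6 | 13.0 / 14.9 |
| 24 | 34.6 | 31.2% / 20.5% | 23.8 / 27.5 | 16.4 / 20.5 |

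Shortfall against the true mean (2020 date to 2019 date):

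- Median 12: 4–10% counted as complete, 14–25% dropped.
- Median 24: 21–31% counted as complete, 41–53% dropped.

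*The unstated rule can decide the figure.* Take four responders, two ended at 4 and 8 months and two ongoing at 20 and 24. All values give (4 + 8 + 20 + 24)/4 = 14.0 months; completed responses only give (4 + 8)/2 = 6.0 months.

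**The case against.** **Row G is leftover text.** The Table 4-2 header makes option (1) a default that the protocol or analysis plan may override, and SAP 3.4 and 4.2.4.4 do specify something else. SAP 4.2.4.3 can be read as governing only the label for the censoring reason. The intent is therefore not in doubt. But no text says row G is overridden, the row names duration of response and offers no alternative, and the protocol agrees with it. The conflict remains.

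**Few patients are affected.** This stands. Rows C2 and F already censor many of the deaths in question.

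**The Kaplan-Meier example is fragile.** This also stands. With eight events the curve lies flat at 0.5 between 10 and 12 months. With the midpoint of the flat segment as the median, the starting value is 11; censoring one of the four shortest gives 12, and censoring the 12-month response one month early gives 13.

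**The Phase I sizes depend on the assumptions.** Agreed. Neither reference date is a stated data cut-off. At a median DOR of 6 months the shortfall is about 1% or less (counted as complete) or 1–5% (dropped). With 58 patients over five dose and schedule groups, sampling noise may exceed the bias, and DOR is also listed by patient.

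**Mean, minimum and maximum were chosen deliberately in SAP Amendment 3, so one clarifying sentence would do.** A sentence would remove the ambiguity. It would not remove the bias, because counting censored values as complete and dropping them both err low.

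**Conclusion.** Both parts hold. Row G contradicts the SAP's own DOR definition and should be corrected, although the intended rule is clear and the affected group is narrow. The Phase I mean is too low whenever a response is censored, under either simple handling; for dropped values this assumes that censoring is unrelated to prognosis.

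The sizes are illustrations. They rest on exponential DOR, the assumed time to response, the two reference dates, administrative censoring only, and for row G an invented set of eight durations or an assumed share q. The Phase I bias is negligible for short responses and substantial for long ones.

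DOR is a secondary, descriptive endpoint in both parts. The primary response rate, PFS and the dose decisions do not change. This should be fixed, but it does not threaten the trial's main conclusions.

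**What to change.** - **SAP Table 4-2, row G:** remove duration of response. Leave row C2 as it is.
- **SAP 3.4:** add one sentence that counting any-cause death as a DOR event departs from protocol 14.1.3.2.5, 14.1.4.5.6 and Table 14-5 row G. Protocol 14.1.4.1 lets deviations be defined in the analysis plan, so no protocol amendment is needed.
- **SAP 3.4.1:** replace the mean with the number of responders, the number ongoing or censored, and the range with censored values marked +. Add a Kaplan-Meier median only where responders suffice, for example by the eight-response guide in SAP 3.4.2.

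The cost is three short SAP wording changes and a small programming check that non-cancer deaths enter DOR as events. The Phase I table would no longer show a mean, and dose groups with few responders would report only counts and ranges.
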